### **Participant Screening and Point of Enrollment**

Participants scheduled to undergo surgery for pelvic organ prolapse (POP) or urinary incontinence will be identified and will be screened against inclusion and exclusion criteria. If confirmed to meet the requirements for the study, they will be eligible to be invited to participate in the study. Participants will be enrolled in the study once informed consent is obtained.

Participants will be enrolled by physicians, fellows, nurse practitioners, physician's assistants, and/or a research nurse prior to surgery. Each practitioner will receive education and training regarding the study enrollment.

## **STUDY POPULATION**

### **Inclusion Criteria**

The study will include women who are seeking surgical management for POP or urinary incontinence.

1. Age greater than 18
2. Creatinine clearance greater than 30 ml/min
3. Failed postoperative hospital voiding trial

### **Exclusion Criteria**

1. Pregnant
2. History of glucose-6-phosphate dehydrogenase deficiency
3. History of renal insufficiency, renal transplant, or nephropathy
4. Allergy to nitrofurantoin

5. History of recurrent UTI (defined as greater than two culture-proven infections in six months or three infections in one year)
6. Urinary Tract Infection (UTI) within one month of surgery
7. Non-English speaking
8. Urinary tract infection while Foley catheter is in place
9. On antibiotic therapy for other non-urological reasons
10. Sustained intraoperative bladder injury requiring prolonged catheterization greater than 5 days
11. Undergoing mesh excision from within the bladder, fistula repair, cystotomy repair, urethral diverticulectomy, sacral neuromodulation, urethral surgery, or any other procedure requiring prolonged catheterization and bladder decompression
12. Placement of a suprapubic catheter
13. Participants that request intermittent self-catheterization
14. Neurologic conditions affecting urinary tract system and normal voiding mechanisms
15. History of hepatic impairment due to prior nitrofurantoin use
16. Inability to provide consent/decisionally impaired
17. More than two in-office voiding trials

### **Rationale for Nitrofurantoin and Regimen Chosen for This Protocol**

Nitrofurantoin was chosen as the interventional medication for this study due to its efficacy in reducing urinary tract infections in women that required short-term postoperative catheterization. Both prophylactic dosing (once daily) and therapeutic dosing (twice a day) have been studied. There are conflicting outcomes with once daily dosing, as one study showed a decrease in UTI rates, while another did not when given during the catheterization time period. There is one study that showed a significant reduction in rate of UTI with twice daily dosing. Therefore, we have decided to proceed with twice daily dosing to ensure maximum coverage for UTI.

Additionally, *Escherichia coli*, the most common uropathogen, displays low resistance patterns to nitrofurantoin in our geographical region. Trimethoprim-sulfamethoxazole (TMP-SMX), another first line therapy for treatment of UTI, which was the agent studied in a prior randomized controlled trial, displays only a 75% sensitivity for treating *Escherichia coli* in our hospital system. Conversely, nitrofurantoin has a 98% sensitivity for treating *Escherichia coli* in our hospital system.

In this study, not all of the participants will be receiving antibiotic treatment during the study course. Per the 2009 International Clinical Practice Guidelines from the Infectious Diseases Society of America (IDSA), prophylactic antimicrobials should not be routinely used in patients with indwelling catheterization due to the concern about selection of antimicrobial resistance. However, they cite that additional studies must be undertaken, given the findings of previous research that does illustrate fewer UTIs in patients who

receive antimicrobial prophylaxis at the time of catheter removal. The data is still evolving regarding prophylactic antimicrobials. We are also limiting the exposure to the antibiotic treatment to only 5 days; recommended treatment courses for nitrofurantoin range from 5-7 days.

### **Study Withdrawal**

Participants may withdraw from the study at any point in time. Documentation of the reason for withdrawal will be captured in the data collection forms. There will be no risk to participants that choose to withdraw from the study.

### **Preoperative Period**

All consecutive participants undergoing a scheduled surgery for POP and/or urinary incontinence will be identified, screened, and approached for enrollment. All will be screened for UTI. To be eligible to participate, the participant is not to have a UTI from 1 day to 1 month prior to surgery. Participants will be asked if they have any dysuria, frequency, or bladder irritation in the absence of vaginal discharge. A “YES” to all three of these symptoms indicates a positive screen, and therefore, the participant will be excluded. Additionally, the participant will be asked if they have been treated for a UTI within the past month with antibiotics. A “YES” indicates a positive screen, and therefore, the participant will be excluded.

Participants who do not meet the inclusion and exclusion criteria will be considered screen failures. Screen failures will be captured and the cause for screen failure will be documented.

### **Perioperative and Surgery Period**

All participants will receive routine preoperative intravenous antibiotic prophylaxis based on standard hospital protocols. This will either be 2 or 3 grams of cefazolin based on patient weight. In the event of an allergy, an appropriate alternative, such as clindamycin 900 milligrams plus aztreonam 2 grams, will be given. All participants will have a 16 French latex Foley catheter placed intraoperatively using sterile technique. Any patient with a latex allergy will receive a non-latex 16 French Foley catheter.

### **Postoperative Period**

All participants will undergo a postoperative retrograde fill voiding trial per our division’s standard protocol on postoperative day zero prior to discharge (for outpatient procedures) or on the morning of postoperative day 1 for hospitalized participants.

Participants will pass the voiding trial if they void more than 200 mL with less than one-third post-void residual. If they fail, a 16 French Foley catheter will be reinserted.

All participants that fail the voiding trial will be discharged home with an indwelling Foley catheter. These participants will receive Foley maintenance education prior to discharge. They will be scheduled for a follow up voiding trial in the office in 1-7 days. The names of all participants that fail the voiding trial will be communicated to the principal investigator and/or the research nurse for continued follow up.

### **In Office Voiding Trial**

Participants who are discharged with an indwelling Foley catheter will be scheduled to return to the office in 1-7 days for an in-office retrograde voiding trial. All office personnel (nurses, medical assistants, physicians, physician's assistants, and nurse practitioners) will receive education regarding voiding trial technique as outlined below prior to study commencement.

The bladder will be retrograde filled with normal saline up to a maximum of 300mL, and the catheter will then be removed. The participant will attempt to void immediately, but the participant will have up to 60 minutes to attempt voiding. After voiding, the participant will be asked to complete a Force of Stream questionnaire. The urine will be measured and a post-void residual will be obtained with a bladder scan. If urine voided is 200 mL or greater, and the post-void residual is less than one-third of the total amount (voided volume plus residual volume), the catheter will be left out and the participant will be considered a voiding trial pass. If the volume is less than 200 mL, and the post-void residual is greater than one third of the total amount, the participant will be deemed a voiding trial failure; these patients will be sent home with a Foley catheter. After completing a bladder scan immediately after voiding attempt, the provider will be notified of the voided volume and post-void residual (to be obtained by bladder scan).

Once a participant has successfully passed the voiding trial, they will be eligible for randomization.

### **Randomization**

Randomization will be controlled by the Carolinas HealthCare System Investigational Drug Services pharmacy through random permuted blocks and stratified per site. The biostatistician will generate the randomization sequence and provide this information to the pharmacist.

The study will be double-blinded such that both study participants and investigators will be masked to treatment allocation and block size randomization, except for the pharmacist and statistician, who will have no contact with the patients.

The Investigational Drug Services (IDS) pharmacy will provide blinded medication bottles containing either nitrofurantoin or placebo 100mg capsules. Each bottle will

contain 10 capsules. These bottles will be labeled by the IDS pharmacy with a randomization number. The study medications will be released by the pharmacy to the research nurse, who is also blinded. The medication bottles will be stored in a locked cabinet in a climate-controlled room until dispensed.

Eligible participants that have successfully passed the in-office voiding trial will be randomized into one of two groups upon completion of the voiding trial data collection sheet. There will be no indication which group the participant was randomized to. These sheets will be fluorescent colored and a part of each participant's chart. This sheet will need to be completed by the nurse administering the voiding trial.

The participants randomized to Group A will receive 100 mg nitrofurantoin every 12 hours by mouth starting on the day the Foley catheter is removed and complete a five-day course. Conversely, participants randomized into Group B will receive a matched placebo every 12 hours each day starting on the date of Foley catheter removal, for five days. Again, there will be no indication which group the participant was randomized to.

At the time of randomization, the participant will be assigned a randomization number. The bottle of medication with the same corresponding randomization ID will be dispensed. This will be a bottle of 10 capsules of nitrofurantoin or matching placebo with instructions to take every 12 hours for five days. The first dose will be given in the office. Participants will be asked to complete a one-week medication diary. Participants will be asked to return this bottle of medication, any unused medication, and a medication compliance diary at the first postoperative visit following surgery.

Any participant that fails the in-office voiding trial will be treated per standard clinical practice. That participant will be scheduled to return for an additional in-office voiding trial in 1-7 days. They will still be eligible to participate in the study after a passed voiding trial in the office. Data will still be collected on these participants. If the participant elects to intermittent self-catheterize, they will then be excluded from the study. Any participant that required any more than two in-office voiding trials postoperatively will be excluded.

### **Week 2 Postoperative Visit (+/- 1 week)**

Participants will be scheduled for a 2-week postoperative follow up visit. They will be instructed to return their bottle of study medication and a medication compliance diary at this visit.

## Treatment of UTIs

Urinary tract infection will be defined as:

- Any treatment received (outside of study drug) for clinically suspected UTI and/or a culture-proven UTI with a uropathogen within the first 30 days following surgery.
  - A urine culture is deemed positive if there are greater than 100,000 colony-forming units of a single organism. Urine cultures with mixed bacterial flora will **NOT** be classified as a positive culture.
  - Clinically suspected UTIs will be defined as dysuria, frequency, and irritation in the absence of vaginal discharge.

Study participants will not be eligible to take phenazopyridine while on study medications.

If a participant has clinical symptoms of a UTI during the study period, a urine specimen will be sent for culture and treatment will be based on appropriate antibiotics regarding specific susceptibilities. Per the IDSA guidelines, the following duration of treatment guidelines will be followed:

- 7-14 days duration of antimicrobial treatment for patients with a catheter-associated UTI, regardless of whether the catheter is in place or not
- A 3-day antimicrobial regimen may be considered for women aged 65 years old or less who develop a catheter-associated UTI after the catheter has been removed

The investigator will maintain discretion to deviate from these guidelines pending clinical reasons.

The participant will be treated empirically for seven days with one of the following antibiotics while awaiting urine culture results, based on personal treatment history, contraindications, and allergies:

- Cephalexin (500mg every 12 hours for 7-14 days) by mouth OR
- Fosfomycin (3 grams once) by mouth OR
- Ciprofloxacin (250 mg every 12 hours for 3 days OR 250-500mg every 12 hours for 7-14 days) by mouth

Fosfomycin is a single dose regimen. Although the IDSA recommends a 3-day or 7-14 day treatment course, recent in-vitro studies indicate that a single dose of fosfomycin is also effective and cost effective. Fosfomycin was demonstrated to have high bactericidal activity against biofilms on siliconized latex catheters. Therefore, it will also be offered as a treatment option for UTI to our participants.

Urine cultures will be obtained with susceptibilities, and antibiotic treatment may be changed depending on resistance. Once the uropathogen is known, the appropriate antibiotic regimen to treat the known uropathogen will be employed.

If a participant is being empirically treated for a UTI, and the urine culture returns negative, the participant will be notified and instructed to stop taking the antibiotics.

The triage nursing staff, both in office and through the nursing phone triage service will receive study training prior to study commencement. Any participant that contacts our office outside of normal business hours with concerns of a UTI will be triaged and empirically treated with one of the appropriate antibiotics listed above. If they receive treatment from another provider outside our hospital system, authorization for release of records will be needed to be signed by the participant.

Any participant that has a positive urine culture from an outside provider, or is treated based on clinical symptoms without evidence of a positive urine culture will be deemed a treatment failure. These participants will be included in the study analysis as treatment failures.

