## STUDY OBJECTIVES

### Primary Objective

To evaluate the efficacy of administration of nitrofurantoin prophylaxis after catheter discontinuation for the prevention of catheter-associated urinary tract infections in patients with postoperative short-term catheterization following pelvic reconstructive surgery. The primary outcome will be the treatment of clinically suspected and/or culture-proven UTI within 30 days of surgery.

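### The primary outcome runs to day 30 after surgery, but the last visit described falls on day 7 to 21 and the readable text sets no outcome check when the window closes

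*Combined protocol and SAP*

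**What the plan says.** The Primary Objective defines the outcome as "treatment of clinically suspected and/or culture-proven UTI within 30 days of surgery". Treatment of UTIs repeats the window and counts any treatment other than study drug for suspected UTI, and/or a "culture-proven UTI with a uropathogen within the first 30 days following surgery". The same section classes a positive culture from an outside provider, or treatment on symptoms alone, as a treatment failure.

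After randomisation one visit is described: "Participants will be scheduled for a 2-week postoperative follow up visit", with a window of plus or minus one week. Its only stated content is return of the bottle and the compliance diary.

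The described routes by which a UTI reaches the study are:
- a culture when a woman has symptoms;
- trained office and telephone triage staff, when she makes contact;
- for care outside the hospital system, a condition that "authorization for release of records will be needed to be signed by the participant";
- under Postoperative Period, the names of women who fail the hospital voiding trial being "communicated to the principal investigator and/or the research nurse for continued follow up".

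The randomisation date varies. After a failed hospital trial on day 0 or 1, "They will be scheduled for a follow up voiding trial in the office in 1-7 days". If that fails, "That participant will be scheduled to return for an additional in-office voiding trial in 1-7 days". "Once a participant has successfully passed the voiding trial, they will be eligible for randomization".

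Statistical Considerations keeps randomised, non-withdrawn women in the intention-to-treat set and limits the per-protocol set to women who finished the study. It gives absence of attrition as one reason for stopping at 164 rather than 180.

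**The concern.** A binary 30-day outcome needs each woman's status to be known at day 30. Here the last described visit can come as early as day 7, and even that visit is not said to ask about UTI. A woman treated elsewhere on day 25 who does not call would, on the text as written, look the same as a woman with no UTI. She has not withdrawn, so she stays in the denominator, and no rule says how unconfirmed status is classed.

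At stake are the two recorded rates, which may be too low, and the meaning of two statements in Statistical Considerations. Completion of the study and absence of attrition both presuppose a contact that establishes them, and none is described.

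A smaller matter is that the visit is anchored to surgery while the course and the one-week diary start at randomisation. A visit early in its window can collect the diary before the course has ended. Secondary Outcome Measures analyses compliance from that diary.

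**Working it through.** The plan states no figure for completeness of day-30 status, so there is none to reproduce. The check is day arithmetic, with surgery as day 0.

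**Window after the visit.** The visit is on day 14 − 7 = 7 to 14 + 7 = 21. Days left to day 30 are 30 − 7 = 23, 30 − 14 = 16 and 30 − 21 = 9.

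**What covers those days.** Triage starts when the woman makes contact. The records release applies once outside care is known, and the text does not say how staff would learn of it. The continued follow-up has neither date nor content. None of these is an outcome check at day 30.

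**Randomisation day r** (Postoperative Period, In Office Voiding Trial, Randomization). With one office trial, r runs from 0 + 1 = 1 to 1 + 7 = 8. With two, it runs from 0 + 1 + 1 = 2 to 1 + 7 + 7 = 15. More than two trials excludes the woman.

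**Diary timing.** The assumptions, which are not in the documents, are: discharge day 0 or 1 equally likely, return days uniform over 1 to 7, and a share q of 10% to 30% needing a second office trial. One trial gives 2 × 7 = 14 equally likely combinations, and two give 2 × 7 × 7 = 98. The mixed share is (1 − q) × one-trial share + q × two-trial share.

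The course is 10 capsules at 12-hour intervals, so the last dose is 4.5 days after the first. Two cut-offs are reasonable for a visit on day V. The broad one counts the course as unfinished if V < r + 5. The strict one counts it only if the visit precedes the last course day, V < r + 4.

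| Visit | Condition | One trial | Two trials | q = 10% | q = 30% |
|---|---|---|---|---|---|
| Day 7 | unfinished, broad (r ≥ 3) | 11/14 = 78.6% | 97/98 = 99.0% | 80.6% | 84.7% |
| Day 7 | unfinished, strict (r ≥ 4) | 9/14 = 64.3% | 94/98 = 95.9% | 67.4% | 73.8% |
| Day 14 | unfinished, broad (r ≥ 10) | 0 | 36/98 = 36.7% | 3.7% | 11.0% |
| Day 14 | unfinished, strict (r ≥ 11) | 0 | 25/98 = 25.5% | 2.6% | 7.7% |
| Day 7 | not yet randomised (r ≥ 8) | 1/14 = 7.1% | 62/98 = 63.3% | 12.8% | 24.0% |
| Day 14 | not yet randomised (r = 15) | 0 | 1/98 = 1.0% | 0.1% | 0.3% |

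For example, the first row at q = 10% is 0.9 × 78.6 + 0.1 × 99.0 = 80.6%. At day 21 every course has ended, since the latest r + 5 is 20.

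**Direction of the effect on the estimate.** The planned measure is the odds ratio. Write p1 for the placebo rate and p2 for the lower treated rate. If the same fraction c of events is captured in each arm, the odds ratio is (p2/p1) × (1 − c·p1)/(1 − c·p2), which moves towards 1 as c falls. If the same number of percentage points x is lost in each arm, the derivative of the log odds ratio at x = 0 is 1/[p1(1 − p1)] − 1/[p2(1 − p2)]. This is negative when p2 < p1 < 0.5, so the odds ratio moves away from 1. The documents do not say which pattern would apply.

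**The case against.** The strongest reply is that absence from the readable text is not absence from the trial. Figure 1, the trial flow, is not shown, and the data collection forms are not reproduced. Randomization speaks of a first postoperative visit, which suggests later ones. Data Collection and Management has research staff recording all study data, and chart review is neither described nor ruled out. A reader might infer that after the visit a UTI is recorded only if the woman calls or signs a release. The documents do not say that these routes are the only ones, so that reading is not supported.

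The endpoint also helps the plan. Its main element is treatment received, which usually follows care-seeking, and the plan trains triage staff and provides for outside records. That is real capture. It does not reach the woman treated elsewhere who tells no one, and it does not set a date on which status is confirmed.

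A reader might also infer that most diaries are returned too early. That needs visits on the first day of the window; at the scheduled day 14 the share is small. Nor may the days before the visit be treated as actively checked for UTI, because no such check is stated.

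Counting the outcome from surgery is a legitimate choice, and randomisation balances the varying time at risk in expectation. Finally, Statistical Considerations is in the past tense, so part of any remedy may come too late. These points limit the finding but do not remove it.

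**Conclusion.** The gap holds as a gap in the described plan. Between 9 and 23 days of a 30-day primary window (16 at the scheduled visit) follow the last described visit, with no stated closing outcome check and no rule for unconfirmed status. Both recorded rates may be too low. The number of missed events cannot be derived, nor can the direction of any effect on the odds ratio.

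A reader might infer bias between the arms. The documents do not support that: participants, investigators and the research nurse are masked, so similar capture in both arms is likely.

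The diary point is minor. Under the stated assumptions the course is unfinished in about 67% to 85% of women at a day-7 visit but only about 3% to 11% at day 14, depending on the cut-off. A visit before randomisation is rarer still.

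The point should be addressed. Confidence is medium, because Figure 1 or the data forms may show a day-30 contact. If one exists, stating it in the text would close the main gap.

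**What to change.** **While follow-up is open.** Add one scripted telephone or portal contact plus a chart check when the 30-day window closes, made by existing masked research staff and asking about UTI treatment from any provider. Tie return of the bottle and diary to a date after the course has ended. The cost is one brief contact per woman, about 164 to 180 in all.

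**If follow-up is complete.** The contact and the re-timed diary return can no longer be added. Do a chart check to day 30 by someone unaware of allocation. The cost is that check and a few lines of reporting.

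**In either case.** State how day-30 UTI status was confirmed, how women with unconfirmed status were classed, and how many there were by arm. Say what marked completion of the study and how attrition was measured. Keep the surgery-anchored primary outcome. A supportive analysis over a fixed period from randomisation is optional; 15 days would be available for every woman, since 30 − 15 = 15 at the latest randomisation day.
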